All patients will be assessed for pain using an 11-point visual analogue scale. Sensory level will be recorded daily as will any episodes of breakthrough pain. Sensory level will be assessed with a change in perception to ice. All assessments will be performed preoperatively, in the PACU (when the patient is deemed to be awake, alert and responding appropriately), and on each subsequent postoperative day until the catheter is removed per the standard nursing epidural policy.

B. Statistical Considerations

Sample Size Justification: Based on the expected differences in efficacy, power analysis was performed (PS software, Vanderbilt University) using $\alpha=0.05$, $\beta=0.80$ and incidence of epidural failure (primary endpoint) difference of 20% (no current studies, estimated from previous experience), we estimate that 91 patients would be needed per group. We would plan to enroll 120 patients per group (240 patients total) to account for drop out due to epidural catheter misplacement, accidental dislodging, or halting of the epidural due to side effects, such as low blood pressure. Drop out rate should be minimal given that all of these patients will be inpatients on surgical wards that will not require post-discharge follow up.

Data Analysis: All continuous data (e.g. secondary endpoints of pain scores) will be assessed for normality using the Shapiro-Wilke test. Comparisons between the primary outcome (epidural failure) will be performed using Fisher's exact test (or chi square depending on effect size). Time to epidural failure for each catheter will be plotted on a failure vs time curve (like a survival curve). Comparison of other outcomes will be performed using the t-test, Mann-Whitney test, Fisher's exact, as appropriate. Duration of epidural analgesia (time to halting) will be analyzed using log-rank analysis. Finally, we will perform a logistic regression to attempt to determine factors that may be associated with epidural analgesia failure. The data will be stored electronically on secure BIDMC servers behind the firewall. The computations will be done using STATA and/or SPSS. The above plan was made in conjunction with biostatistician [name], SCD.

C. Subject Selection

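### The normality check on 11-point pain scores tells the analyst almost nothing, and no comparison of pain scores is adjusted for the preoperative score that is collected

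*Combined protocol and SAP*

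**What the plan says.** Section B3.A (Assessments) sets the pain measure: "All patients will be assessed for pain using an 11-point visual analogue scale". On timing it says "All assessments will be performed preoperatively, in the PACU", and then on each postoperative day until the catheter is removed. Each patient should therefore have one preoperative score and several postoperative scores.

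Section B3.B (Data Analysis) treats pain as a secondary continuous endpoint: "All continuous data (e.g. secondary endpoints of pain scores) will be assessed for normality using the Shapiro-Wilke test". The comparison itself is covered by one general sentence: "Comparison of other outcomes will be performed using the t-test, Mann-Whitney test, Fisher's exact, as appropriate". No time point or summary of the pain score is named. The only regression in the plan is a logistic model for epidural failure, and its covariates are not listed.

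The sample size rests on epidural failure alone. The plan gives no standard deviation, target difference or power for pain scores.

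**The concern.** A normality test followed by a choice between a t-test and a rank test reads as a two-stage rule, although the plan does not write the rule down. On an 11-point integer scale such a check responds to discreteness and bounds. Neither says much about whether a comparison of means would be sound at this sample size. If the check nearly always rejects, it does no work, and the pain comparison becomes an unadjusted rank test.

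Two things are then at stake. One is precision: an unadjusted test of postoperative scores leaves aside whatever the preoperative score predicts. The other is interpretation: the hypothesis in section B1 concerns pain relief, and the plan does not commit to an estimated difference in pain points with a confidence interval.

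**Working it through.** **1. The plan's own figure.** Section B3.B gives "difference of 20% (no current studies, estimated from previous experience" and concludes "we estimate that 91 patients would be needed per group". Inputs: alpha 0.05 (two-sided assumed), power 0.80 (the plan labels it beta), a 20-point difference. The arm rates are not stated, so I assume 40% and 20%.

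- Uncorrected: n = [1.960·√(2·0.30·0.70) + 0.842·√(0.24 + 0.16)]² / 0.20² = 81.2, so 82 per arm.
- Continuity-corrected: n = (81.2/4)·[1 + √(1 + 4/(81.2·0.20))]² = 90.9, so 91 per arm.

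The figure reproduces. It concerns failure, not pain, so it neither supports nor weakens this point. I use 91 per arm below only as the evaluable sample size.

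**2. How often Shapiro-Wilk rejects.** I simulated normal scores rounded to integers and truncated to 0-10. The means and SDs are assumptions, since the plan gives none.

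| Scenario | Rejection rate |
|---|---|
| n = 91, mean 2-5, SD 1.5-2.5 | 83-100% |
| n = 91, mean 4 or below | 98-100% |
| n = 100, mean 2-5, SD about 2 | 91-100% |

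In the n = 91 scenarios the plain t-test kept a type I error of 4.6-5.4%. The check therefore rejects where the t-test is sound.

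**3. Is the two-stage procedure valid?** I ran 2,000 simulations per scenario at 91 per arm, using Mann-Whitney if either arm failed Shapiro-Wilk and the t-test otherwise. Type I error was 0.042-0.054 over six null scenarios. The Monte Carlo standard error is √(0.05·0.95/2000) = 0.005. There is no sign of inflation.

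**4. What baseline adjustment gains.** Let ρ be the correlation between the preoperative score and the postoperative score analysed. Adjustment multiplies the variance by 1 − ρ². I fix the standardised difference that has 80% power unadjusted: 2.80/√(91/2) = 0.415. Adjusted power is then Φ(2.80/√(1 − ρ²) − 1.96).

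| ρ (assumed) | Variance reduction | Power | Equivalent n per arm |
|---|---|---|---|
| 0 | 0% | 80.0% | 91 |
| 0.1 | 1% | 80.4% | 91 |
| 0.2 | 4% | 81.6% | 88 |
| 0.3 | 9% | 83.6% | 83 |
| 0.4 | 16% | 86.4% | 77 |

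The covariate costs one degree of freedom, a variance inflation of about 1/(2·91 − 4) = 0.6%. The table applies to one score per patient. For an average over several days, ρ is the correlation with that average.

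**5. Check by simulation.** Power for a 1-point difference, from the same runs as step 3:

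| Baselines at zero | Observed correlation | Two-stage | ANCOVA |
|---|---|---|---|
| few | 0 | 0.718 | 0.726 |
| most (at least 70%) | 0 | 0.741 | 0.740 |
| most | 0.22 | 0.740 | 0.762 |
| few | 0.29 | 0.741 | 0.784 |
| most | 0.37 | 0.740 | 0.796 |

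With no correlation nothing is gained or lost. Otherwise the gain grows with the correlation, as the formula predicts.

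**The case against.** The strongest reply is that nothing here is wrong. The planned procedure holds its error rate, Mann-Whitney is a conventional choice for a bounded 11-point score, and with no baseline correlation its power matches ANCOVA. All of that stands, so this is an improvement to a valid secondary analysis.

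A reader might infer four stronger things that the documents do not support:

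- **That the data-driven choice of test does harm.** The rule is implied, not written. If the check almost always rejects, the choice hardly varies.
- **That the preoperative score is never used.** The logistic model for failure names no covariates, so preoperative pain could be one of them. What can be said is that no baseline-adjusted comparison of pain scores is specified.
- **That the plan can yield only a p-value.** A rank test can be reported with a Hodges-Lehmann shift in pain points and its interval, and nothing bars summaries by arm. The plan does not commit to any of these.
- **That adjustment is worth a definite number of patients.** This needs a correlation the documents do not give. Their evidence points low: with chronic pain and chronic opioid use excluded, preoperative scores may cluster near zero.

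It is also fair to say that baseline adjustment alone leaves larger gaps. No time point is named. Scores end at catheter removal, and halting or replacing the catheter for lack of pain control is itself primary failure. The fix has to deal with these.

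**Conclusion.** The point holds as a low-cost improvement to a secondary analysis. The Shapiro-Wilk check is uninformative for these scores and in effect selects an unadjusted rank test, while a preoperative score is available and no pain comparison is specified to use it.

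For an assumed ρ of 0 to 0.4, adjustment lowers variance by 0-16% and moves 80% power at 91 per arm to about 80-86%, probably nearer the lower figure. The rejection rates rest on assumed means and SDs for rounded, truncated normal scores.

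The result does not reach the primary endpoint. The Fisher or chi-square test of failure, the 91 per group and the planned enrolment ("We would plan to enroll 120 patients per group (240 patients total) to account for drop out") are unaffected. Even if the precision gain is nil, naming one model in advance and reporting a difference in pain points with an interval remains worthwhile.

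**What to change.** In Data Analysis (section B3.B), remove pain scores from the normality check and specify one analysis:

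- A linear repeated-measures model over the PACU and daily scores, with catheter type, time, their interaction, and the preoperative score as covariate.
- The adjusted mean difference between catheters with a 95% CI, for a contrast named in advance (for example, the average over the PACU and a stated number of postoperative days).
- Mann-Whitney as a sensitivity analysis.
- A rule for missing preoperative scores.
- A statement that scores stop at catheter removal, that removal can itself be primary failure, and how the analysis treats the scores that are then missing.

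The cost is a short paragraph of SAP text and about one degree of freedom for the covariate. The scores are already scheduled, and STATA or SPSS, which the plan names, can fit the model. Sample size and primary analysis stay as they are.

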This will be a double blind, prospective randomized trial to compare the effectiveness of uniport vs multiport thoracic epidural catheters. An investigator will approach patients who are to undergo a surgical procedure with a request for thoracic epidural analgesia. Inclusion criteria will include English speaking, surgery in the thorax or upper abdomen, age between 18 and 75, and expected use of epidural analgesia for >24 hours. Exclusion criteria will include contraindication to epidural catheterization, chronic use of opioids, chronic pain, allergy to the standard medications used for epidural pain relief, incarceration, Body Mass Index >40, delirium, dementia, or other mental status which would make follow-up impossible. All patients will receive informed written consent by an investigator.

After informed written consent is obtained, the patients will be randomized to receive either a flexible multiport catheter or a flexible uniport catheter in the thoracic space. The anesthesia team providing care to the subject will then place the epidural. The APS NP that will follow the subject post operatively will be blinded to the catheter type (these catheters look the same when in place). An appropriate epidural test dose will be used to confirm non-intravenous or intravascular placement. The patient will be assessed for a change in sensory level approximately 10 minutes after administration of test dose to ensure that the epidural catheter is in the epidural space. The epidural will then be taped in place per normal protocol such that the different epidural catheter types will not be identifiable (except for when the epidural is finally removed).

Intraoperative Management:

All epidural infusions will be started intraoperatively at a rate of 6 mL/hr of standard APS 10 epidural solution. The rate of the epidural intraoperatively will then be titrated from 6-12mL/hr at the discretion of the anesthesiologist performing the case. The epidural will not be shut off for hypotension unless the patient is persistently hypotensive despite adequate fluid resuscitation and vasopressor treatment.

Postoperative management:

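### The primary test is unadjusted although surgical site is known for every patient before randomisation; stratifying by site would be a cheap improvement of modest, conditional value

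*Combined protocol and SAP*

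**What the plan says.** The primary outcome is the incidence of failed epidural analgesia (B3.A, Assessments). For its analysis, B3.B (Data Analysis) says: "Comparisons between the primary outcome (epidural failure) will be performed using Fisher's exact test (or chi square depending on effect size"). No stratum or covariate enters that comparison.

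Eligibility requires "surgery in the thorax or upper abdomen" (B3.A, repeated in B3.C and B6), so each patient's surgical site is known at enrolment. B3.A says that patients are randomised to one of two catheter types and describes no stratification.

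The only multivariable analysis is the last one listed in B3.B: "we will perform a logistic regression to attempt to determine factors that may be associated with epidural analgesia failure". It names no covariates and is not tied to the catheter comparison.

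The sample size rests on an "incidence of epidural failure (primary endpoint) difference of 20" per cent, described as "no current studies, estimated from previous experience". From this, "we estimate that 91 patients would be needed per group". Enrolment is set at 120 per group. No failure rate is given for either arm or for either surgical site.

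**The concern.** Failure is defined by lack of pain control. The steps for uncontrolled pain in B3.A turn partly on whether the sensory block covers the painful area, and that area depends on where the operation was. B6 gives a pancreatic resection and a thoracotomy as typical procedures. It is therefore reasonable to suspect that failure rates differ by site.

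If they do, two things follow. Site adds between-patient variation that a stratified test would remove and the planned test leaves in. A chance difference in site mix between arms would also move the observed catheter difference, and the plan names no analysis that takes this into account. B4 hopes that a positive result would change practice well beyond the institution. A reader of such a result is likely to ask whether it survives adjustment for surgical site, and an adjustment chosen after the data are seen answers less well than one chosen in advance.

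**Working it through.** **Inputs from the plan (B3.B).** Two-group comparison; alpha 0.05 (taken as two-sided); power 0.80 (the plan writes this value as beta); difference of 20 percentage points; 91 evaluable and 120 enrolled per group.

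**Assumptions, because the documents give no figure.** Failure rates of 40% and 20%; a 50:50 site mix; randomisation without stratification; a site gap in failure of 0 to 30 points, equal in both arms.

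**Step 1: reproduce the 91.** With 40% versus 20% the mean rate is 0.30. The pooled-variance formula gives

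n = [1.96·√(2·0.30·0.70) + 0.842·√(0.24 + 0.16)]² / 0.20² = 81.2, rounded up to 82.

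The continuity correction gives

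(81.2/4)·[1 + √(1 + 4/(81.2·0.20))]² = 90.9, rounded up to 91.

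This matches the plan, but only once a reference rate is supplied. Without the correction, 47% versus 27% also gives 91.

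**Step 2: variance that stratification can remove.** For a site gap g and a 50:50 mix, the average within-site variance in each arm is p(1−p) − (g/2)². Summed over arms, 0.24 + 0.16 = 0.40 becomes 0.40 − g²/2:

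- g = 10 points: 0.395, a reduction of 1.25%
- g = 20 points: 0.380, a reduction of 5%
- g = 30 points: 0.355, a reduction of 11.25%

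The gain grows with the square of the gap, so small gaps yield almost nothing.

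**Step 3: power by simulation.** 20,000 trials per setting, 91 per arm, 40% versus 20%. The Monte Carlo standard error of each figure is about √(0.85·0.15/20,000) = 0.25 points.

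| Site gap | Chi-square | Site-stratified CMH |
|---|---|---|
| 0 points | 85.0% | 84.9% |
| 10 points | 84.8% | 85.0% |
| 20 points | 84.6% | 86.2% |
| 30 points | 84.7% | 88.3% |

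Fisher's test has about 81% power in every row.

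**Step 4: sensitivity.**

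- At 50% versus 30%, 91 per arm: 79.4% versus 80.8% at a 20-point gap, and 79.4% versus 82.8% at 30 points.
- At 120 per arm, 40% versus 20%, 20-point gap: 92.9% versus 94.1%.
- Site effect expressed as an odds ratio (91 per arm, 40% versus 20%): 84.9% versus 85.4% at an odds ratio of 2, 84.5% versus 86.1% at 3, and 84.7% versus 88.6% at 5.

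**Step 5: type I error.** Null rejection rates, at 91 and 120 per arm with site odds ratios from 1 to 5, were 4.9–5.6% for chi-square, 3.4–4.2% for Fisher and 4.8–5.2% for CMH.

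**Step 6: chance imbalance.** The between-arm difference in site share has standard deviation √(2·0.25/120) = 6.45 points at 120 per arm, and 7.4 points at 91. With a 20-point site gap, a one-SD imbalance at 120 moves the catheter difference by 6.45 × 0.20 = 1.3 points. A 1.96-SD imbalance (12.7 points) moves it by 2.5. For comparison, the unadjusted standard error of the catheter difference at 120 per arm is √(0.40/120) = 5.8 points, and it already contains this source of variation.

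**The case against.** The strongest reply is that an unadjusted Fisher or chi-square test is a valid primary analysis of a randomised binary outcome, and that nothing in the documents says failure differs by site. Both statements are correct. The planned regression only looks for factors that may matter; it does not name site or say that an association is expected.

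A reader might infer that the plan loses power as a matter of fact, or that a site imbalance would bias the result. Neither is supported. The power loss depends on a site effect that is undocumented, and it vanishes when there is none. Chance imbalance adds variance that the test already allows for; it is neither bias nor inflation of alpha (Step 5). Larger gains can be produced by assuming larger gaps, but these become implausible. A 30-point gap already means 35% versus 5% failure in the multiport arm, an odds ratio of about 10. A 40-point gap would require zero multiport failures at one site.

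Two further points stand. Much of the gain over Fisher's test (about 4 points with no site gap) comes from Fisher's conservatism and not from site. The remedy is also not entirely free: B4 allows for operations that involve both regions, so a two-level factor needs a rule.

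What the reply does not remove is the asymmetry. If site is irrelevant, the stratified test costs about 0.1 point of power against chi-square, and it helps if site matters.

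**Conclusion.** The point holds as a cheap improvement, not as a flaw in validity. The primary comparison leaves out a baseline factor that is available for every patient, and the exploratory regression does not fill that gap. Relative to chi-square at 91 per arm, the benefit of stratifying is nil with no site gap, 0.2 points at a 10-point gap, about 1.6 at 20 points and 3.6 at 30 points. Relative to Fisher's test, which the plan names first, it is at least about 4 points. These figures rest on an assumed 50:50 site mix, an assumed 40% versus 20% failure and an assumed site gap. The gain is modest unless site is strongly prognostic, and smaller still if most of the 120 per arm are evaluable.

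**What to change.** In B3.B, pre-specify the primary analysis as a Cochran-Mantel-Haenszel test stratified by surgical site (thorax versus upper abdomen), reported with a Mantel-Haenszel risk difference and 95% confidence interval. State a rule that assigns procedures involving both sites to one stratum, applied from information recorded before randomisation. Keep the unstratified Fisher test as a sensitivity analysis.

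If randomisation has not started, stratify the list by the same factor. The stratified test adjusts for imbalance, but only stratified randomisation prevents most of it. If the investigators prefer the unadjusted test, one sentence saying why would be enough.

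The cost is a sentence or two in the plan, one stratum definition and, where still possible, a two-stratum list. No new data are needed. The downside is a slightly less simple primary test.

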Selection: Patients who are to undergo a surgical procedure with a request for thoracic epidural analgesia will be approached by an investigator. Additionally, the acute pain resident and/or nurse practitioner will look through the daily OR schedule to identify patients that may benefit from thoracic epidurals and discuss with the primary anesthesia team whether this is included in their anesthetic plan. Inclusion criteria will include English speaking, surgery in the thorax or upper abdomen, age between 18 and 75, and expected use of epidural analgesia for >24 hours. We are expecting the racial, ethnic and gender composition of our sample to be representative of the typical BIDMC Boston campus aggregate patient population. Exclusion criteria will include contraindication to epidural catheterization, chronic use of opioids, chronic pain, allergy to the standard medications used for epidural pain relief, incarceration, Body Mass Index >40, delirium, dementia, or other mental status which would preclude providing own informed consent. Women of childbearing age will not be excluded from this study. All patients would receive informed written consent by an investigator.

B4. POSSIBLE BENEFITS

Benefits: Possible benefits include improved pain control following extensive surgical procedures involving the thorax and/or upper abdomen. Our belief is that the smaller/thinner thoracic epidural space will be disproportionately affected by a slightly misplaced end hole (uniport) epidural catheter and that there is a real possibility that the spread of anesthetic solution from a multiport epidural catheter will be superior. If we demonstrate that multiport catheters are superior in our study group this would very likely change standard of care from uniport catheters to using multiport epidural catheters for thoracic epidural analgesia not only at our institution but hopefully on a much larger scale (nation and world wide). Given the many thousands of thoracic epidurals placed annually in the U.S. a 20% (what we're predicting) improvement in analgesia could provide profoundly better pain relief to future post-surgical patients.

B5. POSSIBLE RISKS AND ANALYSIS OF RISK/BENEFIT RATIO

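### The primary test may switch from Fisher's exact to chi-square on effect size, which is not a valid basis for that choice; and β is given as 0.80 where power 0.80 is almost certainly meant

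*Combined protocol and SAP*

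**What the plan says.** Both points are in section B3.B, Statistical Considerations.

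- **Data Analysis.** The comparison of the primary outcome, epidural failure, "will be performed using Fisher's exact test (or chi square depending on effect size"). There is no threshold. The text does not say whether the effect size is the planned or the observed one, or whether the chi-square is continuity-corrected.
- **Sample Size Justification.** With α at 0.05 and β at 0.80, the planning assumption is an "incidence of epidural failure (primary endpoint) difference of 20% (no current studies, estimated from previous experience"). From this, "we estimate that 91 patients would be needed per group". Then: "We would plan to enroll 120 patients per group (240 patients total) to account for drop out". The two failure rates and the sidedness of α are not stated.

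Section B4 repeats the 20% as "a 20% (what we're predicting) improvement in analgesia could provide profoundly better pain relief". That does not settle whether the difference is absolute or relative. No other section clarifies the choice of test or states the power.

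**The concern.** The usual criterion for choosing between Fisher's exact test and chi-square is the expected cell count, not the size of the effect. The wording can be read in three ways, and none gives a usable rule:

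- **Observed effect:** the data choose the primary test.
- **Planned effect:** the choice could be made now, so no exception is needed.
- **Loose wording for cell counts:** the threshold is missing.

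At stake is the conclusion of a borderline trial, where the two tests can fall on opposite sides of 0.05.

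The second point concerns the planning line. β is the type II error, so β=0.80 read literally describes a trial with 20% power. The line on which the sample size rests then does not say what was planned.

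**Working it through.** **Inputs from B3.B:** α=0.05; β as written 0.80; difference 20%; 91 per group needed; 120 per group enrolled. **Assumed, because the plan does not say:** two-sided α; failure rates of 40% vs 20%, with other pairs 20 points apart as the range.

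**1. Reproducing 91 per group.** With p̄ the mean of the two rates and d their difference:

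n = [z(α/2)·√(2p̄(1−p̄)) + z(power)·√(p1(1−p1)+p2(1−p2))]² / d²

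Continuity-corrected: n′ = (n/4)·[1+√(1+4/(n·d))]²

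Power 0.80, 40% vs 20%:
- n = (1.960×0.6481 + 0.8416×0.6325)²/0.04 = 1.8025²/0.04 = 81.2
- n′ = 20.31×(1+√(1+4/16.24))² = 90.9, so **91**

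The pair 80% vs 60% gives the same n′. Without correction, 45% vs 25% gives 89 and 50% vs 30% gives 93.

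**2. Taking β=0.80 literally (power 0.20, z = −0.8416).** For 20 percentage points the largest n is at 60% vs 40%:
- n = (1.960×0.7071 − 0.8416×0.6928)²/0.04 = 0.8028²/0.04 = 16.1
- n′ = 25.1, so at most 26 per group (one-sided: 16.9, so 17)

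On the absolute reading, 91 therefore cannot come from 20% power. On a relative reading (40% vs 32%, d=0.08), literal power 0.20 gives 0.7611²/0.0064 = 90.5 uncorrected, also 91. At power 0.80 the same relative pair needs 564 (589 corrected).

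**3. Can the tests disagree?** With n per arm, x and y failures and D = |x(n−y) − y(n−x)|:

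χ² = 2n·D² / [n²(x+y)(2n−x−y)], with D replaced by D−n for the corrected version.

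- 36 vs 23 of 91: D = 36×68 − 23×55 = 1183. χ² = 182×1183²/(91²×59×123) = 4.24, p=0.040. Corrected: D−91 = 1092, χ² = 3.61, p=0.057. Fisher p=0.057.
- 48 vs 33 of 120: D = 48×87 − 33×72 = 1800. χ² = 240×1800²/(120²×81×159) = 4.19, p=0.041. Fisher p=0.056.

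**4. How often?** Exact binomial enumeration of every table, two-sided 0.05:

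| | 91 per arm | 120 per arm |
|---|---|---|
| Tables in all | 8,464 | 14,641 |
| Significant by uncorrected chi-square only | 164 | 234 |
| Significant by Fisher only (vs uncorrected) | 0 | 0 |
| Trials disagreeing, 40% vs 20% | 3.9% | 2.0% |
| Trials disagreeing, maximum over 20-point gaps | 4.9% | 3.0% |
| Largest type I error, Fisher | 3.7% | 3.9% |
| Largest type I error, uncorrected chi-square | 5.2% | 5.4% |
| Significant by Fisher only (vs corrected) | 8 | 4 |
| Significant by corrected chi-square only | 0 | 0 |
| Trials disagreeing, Fisher vs corrected, maximum over 20-point gaps | 0.6% | 0.3% |

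Every table that is significant by Fisher is also significant by uncorrected chi-square. Always taking the more favourable of those two therefore has the type I error of chi-square alone.

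**5. Power by test (Fisher / uncorrected / corrected):**
- 40% vs 20%: 80.8 / 84.7 / 80.2% at 91; 90.8 / 92.9 / 90.8% at 120
- 60% vs 40%: 71.4 / 76.3 / 71.4% at 91; 83.9 / 86.9 / 83.9% at 120

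**The case against.** The case for leaving the text alone is that Fisher is already named as the default, the harm needs an uncorrected chi-square to be meant, and even then error control is barely touched. Those facts stand and limit the point to a minor one. They do not supply the missing rule: the same table of 36 vs 23 gives p=0.040 or 0.057 depending on which chi-square is meant.

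It is also fair that naming any single test, or an expected-count rule, would cure the ambiguity. Keeping Fisher is the smallest edit, not the only valid one.

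Three stronger readings are tempting, and the documents do not support them:

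- **The switch materially inflates the false-positive rate.** It does not. The ceiling is about 5.4%, even if the favourable test is always taken.
- **Sparse cells could make chi-square invalid here.** Under the plan's assumption, read as 20 percentage points, the mean of the two rates is at least 10%. The smallest expected count is then at least 0.10×91 = 9.1, or 0.10×120 = 12, above the usual threshold of 5. Rarer failure is possible, since the difference is "no current studies, estimated from previous experience", but nothing in the plan points to it.
- **β=0.80 shows that the trial is underpowered or that 91 is wrong.** Power 0.80 with a plausible pair of rates gives 91 exactly, so the label is at fault rather than the number. Certainty is not available, because literal 20% power with a relative 20% reduction (40% vs 32%) also rounds to 91. A trial designed for 20% power is a far less likely intention, but this is why the sponsor should confirm the meaning of 20%.

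**Conclusion.** Both points hold, at minor severity. The plan gives an invalid and possibly result-driven basis for leaving its named primary test. If an uncorrected chi-square is meant, that can turn a borderline non-significant result into a significant one, never the reverse, in at most 4.9% of trials at 91 per arm and 3.0% at 120 for any 20-point difference. If a continuity-corrected chi-square is meant, the issue almost disappears.

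The β value is wrong as a description of the design and is almost certainly a label slip; no patient number changes.

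The figures assume two-sided testing at 0.05. The 40% vs 20% results also assume those rates, which the plan does not give. That effect size is the wrong criterion, and that β=0.80 literally means 20% power, depends on neither assumption.

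**What to change.** - **Data Analysis:** delete the parenthetical chi-square alternative and keep Fisher's exact test as the single primary test. The sponsor should confirm and state its sidedness, which the plan leaves open.
- **Sample Size Justification:** replace the β value with power 0.80 (β=0.20). The sponsor should confirm from its own power calculation whether the 20% difference is absolute or relative, and state the answer.

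Both edits should be made before outcome data are examined.

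**Cost:** wording only, with no extra patients. Against an uncorrected chi-square, Fisher gives up about 4 points of power at 91 evaluable per arm (80.8% vs 84.7%) and about 2 at 120 (90.8% vs 92.9%), at 40% vs 20%. If the rates were nearer 60% vs 40%, Fisher would have 71.4% at 91 and 83.9% at 120, against 76.3% and 86.9%. Against a continuity-corrected chi-square nothing is lost. If the sponsor prefers chi-square, naming it alone and stating whether it is continuity-corrected would also close the gap.
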